8.3 Analytical tools

All statistical analyses are carried out in R software. Statistical tests are two-sided, and $p < 0.05$ is considered statistically significant.

9. Criteria for Participant and Study Completion and Premature Study Termination

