3.2 Primary and Secondary Outcomes

The primary outcomes for respiratory health are lung function indicators, including forced expiratory volume in 1 s (FEV₁), forced vital capacity (FVC), FEV₁/FVC ratio, peak expiratory flow (PEF), forced expiratory flow at 25–75% of FVC (FEF_{25-75%}), maximal expiratory flow at 75% of FVC (MEF_{75%}), maximal expiratory flow at 50% of FVC (MEF_{50%}), and maximal expiratory flow at 25% of FVC (MEF_{25%}); changes of FeNO; Changes of FeCO. The primary outcomes for cardiovascular health are blood pressure indicators, including systolic blood pressure (SBP), diastolic blood pressure (DBP), mean arterial pressure (MAP) and pulse pressure (PP); heart rate variability indicators, including standard deviation of all normal-to-normal intervals (SDNN), the root mean square of successive differences between adjacent normal cycles (rMSSD), the percentage of adjacent NN interval differences greater than 50 ms (pNN50), very low frequency (VLF), low frequency (LF), high frequency (HF), the ratio of LF to HF (LF/HF); and electrocardiograph parameters, including the interval of the beginning of the P wave to the beginning of the QRS complex (PR interval), the interval of the beginning of Q wave to the end of the S wave (QRS duration), the interval from the onset of the QRS complex to the end of the T wave (QT interval), the QT correction for rate (QTc interval), amplitude of the R wave in lead V5 (RV5), S-wave depth in lead V1 (SV1) and the sum of the R-wave amplitude in lead V5 and the S-wave amplitude in lead V1 (RV5+SV1). The primary outcomes for cognitive health are academic performances, including standardized scores and relative ranking of scores.

The secondary outcomes include the metabolites in exhaled breath condensate, serum protein, the indicators measured by the Wisconsin Card Sorting Test, Attention Network Test, and N-BACK Test. Furthermore, other omics and targeted biomarkers of interest (e.g., CRP, 8-OHdG, etc) are also considered.

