8.2 Analytical models

We use a linear mixed-effects model to estimate the effects of air purification intervention or per interquartile range (IQR) decrease in personal PM_{2.5} exposure on several functional indicators and targeted biomarkers of children's health. To account for the impact of varied outcome levels at baseline, the absolute or relative change in outcome level is calculated as the difference between post-intervention and pre-intervention, comparing the change in health outcomes between the intervention and control groups after the intervention. We further adjusted for the confounders including sex, age, body mass index (BMI, kg/m²), temperature (°C), relative humidity (%), etc. A random intercept for each participant is included in the models to account for the repeated measurements.

In addition, we plan to perform metabolomics analysis of EBC samples using ultra-high performance liquid chromatography-tandem mass spectrometry and proteomic analysis of serum samples with 4D-label free technology. Besides, other omics analyses and targeted biomarkers of interest are planned to further explore the potential biological mechanisms.

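### Sections 8.2 and 8.3 give the EBC metabolomics and serum proteomics secondary outcomes no statistical test and no false-discovery control; the only rule, p<0.05 per test, passes about 5% of unaffected features

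*Combined protocol and SAP*

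**What the plan says.** Section 3.2 lists the omics measurements among the secondary outcomes: "The secondary outcomes include the metabolites in exhaled breath condensate, serum protein, the indicators measured by the Wisconsin Card Sorting Test", followed by the other two cognitive tests. It adds that "other omics and targeted biomarkers of interest (e.g., CRP, 8-OHdG, etc) are also considered". The synopsis lists the same items as secondary endpoints.

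Section 8.2 gives the laboratory methods. For the breath samples it says: "we plan to perform metabolomics analysis of EBC samples using ultra-high performance liquid chromatography-tandem mass spectrometry". Serum goes to label-free proteomics. The linear mixed model in the same section is described for functional indicators and targeted biomarkers, with two kinds of effect: that of the purification intervention, and that per interquartile-range (IQR) decrease in personal PM2.5. No statistical test is named for the metabolomic or proteomic data.

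Section 8.3 supplies the only decision rule: "All statistical analyses are carried out in R software. Statistical tests are two-sided, and $p < 0.05$ is considered statistically significant". It makes no exception for any family of outcomes. No section mentions a multiplicity adjustment, a false-discovery rate, a testing hierarchy or a validation step.

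**The concern.** A 5% rule per test suits a single pre-specified comparison. Metabolomics and label-free proteomics normally return many features per sample, and a 5% rule applied to each will pass a steady share of them even if purification does nothing. A published list of changed metabolites and proteins, and any mechanism built on it, could then be made up largely or wholly of chance findings, with nothing fixed in advance to tell the two apart.

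The gap is separate from multiplicity among the primary outcomes. A rule written for the primaries would leave these families uncovered, and screens of this size call for a different tool. The cognitive secondaries fall under the same unadjusted rule, on a smaller scale.

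**Working it through.** The threshold is a stated rule, so the plan has no figure to reproduce on this point.

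**Inputs from the documents.** Two-sided p<0.05 per test (8.3); EBC metabolites and serum protein as secondary outcomes (3.2); metabolomics and label-free proteomics platforms (8.2); 14 Wisconsin indices (glossary); six N-back tests (7.11.3); 128 Wisconsin stimulus cards (7.11.2).

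**Assumed inputs.** Number of features m, share truly changed π, power per feature, correlation r between test statistics, and three Attention Network scores.

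**Step 1. Expected false declarations if no feature changes.** The expectation is 0.05 × m, and correlation between features does not alter it. The ranges assume independence; correlation would widen them.

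| m (assumed) | Expected false | 95% range if independent |
|---|---|---|
| 50 | 2.5 | 0–6 |
| 100 | 5 | 1–10 |
| 200 | 10 | 4–16 |
| 500 | 25 | 16–35 |
| 1000 | 50 | 37–64 |

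**Step 2. Chance of at least one false declaration.** Under independence this is 1 − 0.95^m. For equal correlation r it was found by numerical integration.

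| m | r = 0 | r = 0.5 | r = 0.8 |
|---|---|---|---|
| 50 | 0.92 | 0.62 | 0.30 |
| 200 | >0.99 | 0.90 | 0.42 |

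Even a small panel with strongly correlated features is well above 0.05.

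**Step 3. Share of declared features that are false.** This is (1 − π) × 0.05 / [(1 − π) × 0.05 + π × power].

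- π = 0.05, power 0.5: 0.0475 / (0.0475 + 0.025) = 0.655, about 66%.
- π = 0.10, power 0.8: 0.045 / (0.045 + 0.08) = 0.36.
- π = 0.01, power 0.3: 0.0495 / (0.0495 + 0.003) = 0.94.

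**Step 4. Effect of Benjamini-Hochberg at 5%.** Simulation with 2000 runs per setting, independent features, 5% truly changed with mean z of 3 (assumed):

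| m | False declarations, p<0.05 | False declarations, adjusted |
|---|---|---|
| 200 | 9.5 | 0.3 |
| 500 | 23.8 | 0.6 |
| 1000 | 47.1 | 1.0 |

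The false share of declared features falls from about 52% to about 5%. The unadjusted share is below the 66% of step 3 because a mean z of 3 implies power of about 0.85: 0.0475 / (0.0475 + 0.05 × 0.85) = 0.53.

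**Step 5. Cognitive secondaries.** At most 14 + 6 + 3 = 23 tests. Six Wisconsin indices are percentage versions of other indices. If all 128 cards are given, each such pair is one test, and total correct and total errors are complements. That leaves 14 − 6 − 1 = 7 Wisconsin tests, so 7 + 6 + 3 = 16.

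| Tests | r = 0 | r = 0.5 | r = 0.8 |
|---|---|---|---|
| 16 | 0.56 | 0.37 | 0.21 |
| 23 | 0.69 | 0.45 | 0.24 |

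The columns at 0.5 and 0.8 are the fairer guide, because these indices cannot be independent.

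**The case against.** **Silence is not a rule against adjustment.** A reader might infer that 8.3 imposes an unadjusted 5% level on all analyses. The text does not say so. The word for all belongs to the software sentence, "All statistical analyses are carried out in R software", and the p<0.05 sentence neither calls the p-values unadjusted nor excludes adjusted ones. This objection stands: the defect is an omission. It still matters, because p<0.05 is the only rule available to anyone following the plan.

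**No feature-by-feature screen is written down.** This is also true. Section 8.2 names platforms for the omics data and no test. The objection limits what can be said about what the trial would report, but it shows that neither test nor threshold is fixed in advance, which widens the gap.

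**Untargeted analysis and tens of false hits are not in the text.** The documents use no such term and give no feature count. That the platforms are untargeted is a reasonable inference, since 8.2 lists targeted biomarkers separately, but it remains an inference. An expected count of ten or more needs about 200 features; 50 to 100 features would give 2.5 to 5.

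**The omics may be meant as exploratory.** Section 8.2 ends by saying that other omics and targeted biomarkers will further explore mechanisms, and the trial's overall aim is worded as exploration. Many statisticians accept unadjusted secondary analyses when they are labelled exploratory. Here the label is missing: the sentence concerns the other omics, while 3.2 and the synopsis list metabolites and serum protein as secondary outcomes.

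**The cognitive tests overlap.** This stands, and is why 16 is shown beside 23. The documents also do not say that every index in the glossary will be tested.

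**Conclusion.** The concern holds as an omission with a predictable consequence. The metabolomic and proteomic secondary outcomes have no named test and no false-discovery control, and the one rule in the plan would pass about 5% of unaffected features. That rate follows from the rule alone and does not depend on correlation. The counts (2.5 of 50 up to 50 of 1000) rest on assumed panel sizes. The false share of about 66% rests on assumed values for the proportion truly changed and for power, and runs from 36% to 94% over 1–10% truly changed and 30–80% power.

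The documents do not support the stronger claim that tens of features will be falsely declared, or that the plan rules out adjustment.

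For the cognitive secondaries the family-wise rate is about 0.2 to 0.45 at correlations of 0.8 to 0.5, with roughly 16 to 23 tests. This is above 0.05, but how to group or label them is a lesser choice for the sponsor. The omics gap should be closed; because these are secondary outcomes, it does not threaten the primary conclusions.

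**What to change.** 1. In 8.2, name the statistical test for the omics features, for example the mixed model already used for the functional indicators.
2. In 8.3, state that for each omics platform a feature is declared changed only if its Benjamini-Hochberg adjusted p-value, taken over all features that pass quality control on that platform, is below 0.05.
3. Apply the adjustment separately to the true-versus-sham contrast and, if it is used for omics, to the contrast per IQR decrease in PM2.5.
4. Do this before any pathway or mechanism analysis.
5. Say how the cognitive secondaries are to be grouped, adjusted or labelled. The choice is the sponsor's.

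The cost is a few sentences across the two sections, the specification of the omics model, and a short adjustment step in R. No new data or participants are needed. Fewer features will be declared significant, and power for any single feature will be lower.

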Official Title: The Health Benefits of Indoor Air Filtration Among Children

NCT Number: NCT04835337

Document Date: 2024-09-12

Protocol Synopsis

Title	The Health Benefits of Indoor Air Filtration Among Children
Intervention	Classroom and household air purifiers
Study Objectives	This study aims to explore the health benefits of air purifiers on children's health.
Study Design	The study is a randomized, controlled, double-blind, crossover trial of a multi-setting air purification intervention.
Primary Endpoint(s)	The primary outcomes are cardio-respiratory function including lung function, airway inflammation, blood pressure, heart rate variability, electrocardiograph, academic performances including standardized scores and relative ranking of scores.
Secondary Endpoint(s)	The secondary outcomes are metabolites in exhaled breath condensate, serum protein, cognitive function measured by Wisconsin Card Sorting Test, Attention Network Test, and N-BACK Test, other omics and targeted biomarkers of interest (e.g., CRP, 8-OHdG, etc).
Accrual Objective	105
Study Duration	9 months (from April 2021 to December 2021)
Treatment Description	Participants are divided into an intervention group and a control group according to the principle of cluster randomization. The intervention group is equipped with true-particulate air purifiers and the control group is equipped with sham-purification devices in households and school classrooms.
Inclusion Criteria	(i) Fourth-grade students (10–12 years old) in primary school; (ii) no plans to change schools during the current school year; (iii) those who participate voluntarily and are able to undergo questionnaires and health checks; and (iv) those who have good compliance and accept the installation of an air purifier and PM _{2.5} monitoring equipment at home.
Exclusion Criteria for Individual	(i) transferring schools expected during the study period; (ii) having a chronic disease diagnosed by a doctor within the past year.

Glossary of Abbreviations	5
1. Background and Rationale.....	6
2. Study Objectives.....	6
3. Study Design	6
3.1 Description of Study Design.....	6
3.2 Primary and Secondary Outcomes.....	6
3.3 Stratification, Randomization, and Blinding	6
4. Participants and Sites.....	7
4.1 Inclusion Criteria	7
4.2 Exclusion Criteria for Participant	7
4.3 Sites	7
5. Known and Potential Risks and Benefits to Participants.....	7
6. Intervention	7
6.1 Intervention	7
6.2 Washout Period.....	8

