rMSSD	Root mean square of successive differences between adjacent normal cycles
pNN50	Percentage of adjacent NN interval differences greater than 50 ms
VLF	Very low frequency
LF	Low frequency
HF	High frequency
LF/HF	Ratio of LF to HF
PR interval	The interval of the beginning of the P wave to the beginning of the QRS complex
QRS duration	The interval of the beginning of Q wave to the end of the S wave
QT interval	The interval from the onset of the QRS complex to the end of the T wave
QTc interval	The QT correction for rate
RV5	Amplitude of the R wave in lead V5
SV1	S-wave depth in lead V1
RV5+SV1	The sum of the R-wave amplitude in lead V5 and the S-wave amplitude in lead V1

1. Background and Rationale

Previous studies have suggested that fine particulate matter (PM_{2.5}) has adverse effects on children's respiratory, cardiovascular, and cognitive health. However, it is not clear whether reduced PM_{2.5} concentration by indoor air purifiers is beneficial for the multi-system health of school-age children.

2. Study Objectives

This study aims to explore the health benefits of air purifiers on children's health.

3. Study Design

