7.7 Blood pressure measurement

After a 5-minute rest in a quiet environment, the child-appropriate BP cuff is wrapped around the left upper arm of the children to measure BP using the Omron electronic sphygmomanometers (OMROM, J751). BP is measured at 2-minute intervals, with a total of three measurements taken. If the difference in BP values between the last two measurements exceeds 5 mmHg, additional measurements are performed. Each child is allowed to measure BP at least three times and up to five times. The SBP, DBP and heart rate are recorded; the mean arterial pressure (MAP) and pulse pressure (PP) are calculated. The HOBO thermo-hygrometer is set up in the medical examination room to monitor the temperature and relative humidity.

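### Section 3.2 names 30 unranked primary outcomes in three domains, and Section 8.3 tests each at p<0.05 with no multiplicity procedure: 0.5 respiratory, 0.9 cardiovascular and 0.1 academic chance findings are expected if nothing is affected

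*Combined protocol and SAP*

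**What the plan says.** Section 3.2 sets out primary outcomes in three groups.

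- **Respiratory:** "The primary outcomes for respiratory health are lung function indicators", of which eight are listed, followed by "changes of FeNO; Changes of FeCO".
- **Cardiovascular:** "The primary outcomes for cardiovascular health are blood pressure indicators" (four), then seven heart rate variability and seven electrocardiograph parameters.
- **Academic:** "The primary outcomes for cognitive health are academic performances, including standardized scores and relative ranking of scores".

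The Protocol Synopsis gives the same material by category ("The primary outcomes are cardio-respiratory function including lung function, airway inflammation, blood pressure, heart rate variability, electrocardiograph", then academic performance), also without an order. Section 7.10 divides the standardised scores into maths, Chinese and total, and adds ranking within the grade.

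The decision rule is one sentence in Section 8.3: "Statistical tests are two-sided, and $p < 0.05$ is considered statistically significant". Section 8.1 uses the same 0.05, undivided, and names no outcome that drives the sample size. Section 8.2 allows an intervention effect or an effect per interquartile-range fall in personal PM2.5, and an absolute or a relative change. No section mentions a hierarchy, a co-primary rule, family-wise control or false discovery control.

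Section 2 states the aim: "This study aims to explore the health benefits of air purifiers on children's health".

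**The concern.** Calling an outcome primary tells the reader that a significant result on it answers the trial's question. Here 30 outcomes carry that label and each is judged alone at 0.05. The plan does not say how many must succeed, or which, before a benefit is claimed for lung function, the heart or school performance. A report could follow the plan exactly, find one significant cardiovascular primary out of 18, and present it as a primary finding, although about one is what chance alone would be expected to produce. The reader would have no stated rule for telling the two situations apart.

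**Working it through.** **Count, from Section 3.2.** Respiratory: 8 lung function + FeNO + FeCO = 10. Cardiovascular: 4 blood pressure + 7 heart rate variability + 7 electrocardiograph = 18. Academic: scores + ranking = 2. Total 10 + 18 + 2 = 30. If the three scores in Section 7.10 are tested separately with one ranking (assumed), the academic set is 4 and the total 32; with three rankings (assumed), 6 and 34. The plan gives no count or overall error rate of its own to reproduce.

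**Expected chance findings.** With k tests at level 0.05, no true effect and valid p-values, the expected number is k × 0.05. Expectations add under any correlation, so no independence assumption is needed. The chance of at least one does depend on correlation: it is 1 − 0.95^k if tests are independent. For correlated tests I used equicorrelated normal statistics, with an assumed correlation of 0.9 within each domain and independence between domains.

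| Set | k | Expected | At least one, independent | At least one, assumed correlation 0.9 |
|---|---|---|---|---|
| Respiratory | 10 | 0.5 | 40% | 13% |
| Cardiovascular | 18 | 0.9 | 60% | 15% |
| Academic | 2 | 0.1 | 10% | 7% |
| All | 30 | 1.5 | 79% | 31% |

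With 32 to 34 tests, the overall expectation is 1.6 to 1.7 and the academic one 0.2 to 0.3.

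Some primaries are functions of others. Section 7.7 says that "the mean arterial pressure (MAP) and pulse pressure (PP) are calculated", and FEV1/FVC, LF/HF and RV5+SV1 are of the same kind. This makes chance findings cluster. It changes the last two columns but not the expected number.

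**Which family to control.** I compared Benjamini-Hochberg at 5% over all 30 with the same procedure run within each domain. Assumptions: independent tests, every outcome in the respiratory or the cardiovascular domain truly affected at 80–90% power per test at 0.05, and nothing affected elsewhere.

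| | Pooled over 30 | By domain |
|---|---|---|
| Any false claim in the other two domains | 21–28% | about 10% |
| Power per outcome in the affected domain | 60–85% | 77–89% |

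Pooling lets strong results in one domain relax the threshold in another.

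**Cost in power.** The documents give no power, so 80% at 0.05 is assumed, which means a standardised effect of 1.96 + 0.84 = 2.80. If one outcome in a domain is affected, the first-step thresholds are 0.05/10 = 0.005, 0.05/18 = 0.0028 and 0.05/2 = 0.025. Simulated power for that outcome is about 51%, 44% and 72% for the respiratory, cardiovascular and academic sets (repeat runs differ by about a percentage point). If a whole respiratory or cardiovascular domain is affected, it is about 77%. Holm over all 30 starts at 0.05/30 = 0.0017, with about 37% power for a single affected outcome.

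**Trial-wide error with control by domain.** Under the complete null with independent tests, 1 − 0.95³ = 14%.

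**The case against.** The strongest reply is that this is exploratory work. Section 2 says so, Section 3.2 sets out three separate outcome sets, and Section 8.1 cites sizing literature for the same three areas. Nothing states a single trial-wide claim, so 1.5 and 79% answer a question that the plan does not pose. This is right as far as it goes: the domain is the natural family, and the domain figures should lead. It does not remove the problem, because the expected number is still 0.5 for respiratory and 0.9 for cardiovascular outcomes. If exploration is meant, the plan should label nominal results as exploratory. Instead it calls the outcomes primary and declares significance at 0.05.

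A second reply is that the outcomes are strongly related, so the independence figures overstate the risk of any false positive. This also stands. The documents give no correlations, and at an assumed 0.9 the domain figures fall to 13%, 15% and 7%. The expected number does not fall.

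A reader might infer more than this:

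- **That a false primary finding is more likely than not.** This depends on the correlation. The overall figure is 79% with independence but 31% at an assumed 0.9 within domains.
- **That results were seen or selected before the list was written.** The document is dated 2024-09-12 and the study ran from April to December 2021, but neither date shows that any p-value existed or that any outcome was chosen by result.

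**Conclusion.** The concern holds, by domain. Thirty unranked primaries and one unadjusted threshold mean that a plan followed to the letter is expected to yield 0.5 respiratory, 0.9 cardiovascular and 0.1 academic chance findings (1.5 in all) if nothing is affected. That result rests only on the count, on one test per outcome and on valid p-values. The probabilities of at least one chance finding also rest on assumed correlations, and the power figures on an assumed 80–90% and independent tests.

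The number of tests is a minimum, because Sections 7.10 and 8.2 leave the academic components, the change scale and the exposure model open. This should be corrected, since it bears on how every primary result is read. It does not show that any particular result is false.

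**What to change.** In Section 8.3, replace p<0.05 for the primary outcomes with one fixed procedure: Benjamini-Hochberg at a 5% false discovery rate, run separately within the respiratory, cardiovascular and academic sets of Section 3.2. Apply it to:

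- a closed test list, with every outcome named in Section 3.2, the academic scores and rankings of Section 7.10 listed one by one, and one change scale (absolute or relative) per outcome;
- the randomised true-versus-sham contrast only, with the per-IQR PM2.5 models reported as supportive.

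Label primaries that reach only nominal p<0.05 as exploratory. Do not choose a lead outcome or the procedure according to results. The document postdates the study period, so a lead outcome named now would be open to that doubt, whereas a procedure over the full list selects no outcome.

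The change is to wording and reporting; no new data are needed. The price is the lower power per outcome shown above, and control of about 5% per domain, hence about 14% across the trial under the complete null. If 5% trial-wide is wanted, Holm over the full list gives it, at about 37% power for a single affected outcome.

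No such procedure repairs invalid p-values. Classes are randomised (Sections 3.3 and 7.2), but the only random effect named in Section 8.2 is a participant intercept. The stated rates need the model to reflect the class randomisation, which is a separate point.
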